4.2.2 SECONDARY ENDPOINTS

- 1) Systolic BP change: measured on a per-treatment basis; defined as pre-HD – nadir intra-HD systolic BP (mmHg)
- 2) Nadir systolic BP: measured on a per-treatment basis; defined as the minimum intradialytic systolic BP (mmHg)
- 3) Target weight achievement: measured on a per-treatment basis: defined as post-HD weight within 1 kg of prescribed target weight.
- 4) Weight difference: measured on a per-treatment basis; defined as target weight – post-HD weight (kg)
- 5) Patient acceptance: measured after treatment 9 of each phase; response to the following question, "If recommended by your physician, would you be willing to adopt the HD prescription you have received during the last 9 treatments?"

6) TTE ejection fraction (EF): measured 30 minutes before HD end during 7th treatment in the first phase of each treatment type (once during conventional and once during UF profiled treatment); defined as % EF change (baseline – intradialytic EF), see Appendix A for TTE protocol

7) Patient-reported symptoms: measured after the 1st HD treatment each week; see Appendix B for data collection form.

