10.4 DESCRIPTION OF STATISTICAL METHODS

10.4.1 GENERAL APPROACH

By cross-over design, each participant will act as his or her own control, permitting between and within group comparisons. Analyses will be performed on an intention-to-treat and modified intention-to-treat basis, separately. Comparisons of values between HD treatments will be performed by repeated-measures analysis of variance (ANOVA; or non-parametric methods depending on data type) for continuous outcomes and generalized estimating equations for categorical outcomes. Analogous analyses will be performed in both the intention-to-treat and modified intention-to-treat datasets. All statistical estimates will be tabulated along with their corresponding 95% confidence intervals. All reported P values will be 2-sided; <0.05 representing significance. All hypothesis tests that are observed to be statistically non-significant will be interpreted as such and reported as being inconclusive. However, as this is a small, pilot study, the magnitude of estimates and the corresponding confidence intervals will be considered in the results interpretation.

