10.4.3 ANALYSIS OF THE SECONDARY ENDPOINT(S)

Comparisons of values for the binary secondary endpoints of target weight achievement, patient acceptance, and symptom occurrence between HD treatments will be performed using generalized estimating equations. Comparisons of values for the continuous secondary endpoints of pre-HD to nadir intradialytic HD systolic BP change, intradialytic nadir systolic BP change, target and post-HD weight difference, and TTE ejection fraction change will be performed using ANOVA or non-parametric methods depending on data type.

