Appendix B: Symptom Monitoring Questionnaire

PATIENT-REPORTED SYMPTOMS DURING DIALYSIS

INSTRUCTIONS

Please respond to each statement by marking one box per row.

We are interested in the symptoms you had DURING your dialysis treatments LAST WEEK. Respond ONLY based on the dialysis treatments last week.

During your dialysis treatments last week, did you have CRAMPING?
	No cramping 	Mild cramping 	Moderate cramping 	Severe cramping 	Very severe cramping 
--	---	---	---	---	--

During your dialysis treatments last week, did you have NAUSEA or UPSET STOMACH?
	No nausea 	Mild nausea 	Moderate nausea 	Severe nausea 	Very severe nausea 
---	---------------------------------------	---	---	---	--

During your dialysis treatments last week, did you have VOMITING or THROWING UP?
	No vomiting 	Mild vomiting 	Moderate vomiting 	Severe vomiting 	Very severe vomiting 
---	---	---	---	---	--

During your dialysis treatments last week, did you have
 
DIZZINESS or LIGHTHEADEDNESS?
	No dizziness 	Mild dizziness 	Moderate dizziness 	Severe dizziness 	Very severe dizziness 
---	--	--	--	--	---

During your dialysis treatments last week, did you have
 
RACING HEART or HEART PALPITATIONS?
	No racing heart 	Mild racing heart 	Moderate racing heart 	Severe racing heart 	Very severe racing heart 
---	---	---	---	---	--

During your dialysis treatments last week, did you have
 
CHEST PAIN?
	No chest pain 	Mild chest pain 	Moderate chest pain 	Severe chest pain 	Very severe chest pain 
---	---	---	---	---	--

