Depending on the type of various endpoints, we propose to perform the following tests to test the difference between UF profile and conventional treatment.

- **Binary Outcomes**
 - We will perform repeated measure logistic regression by regressing the binary outcome on the treatment indicator and test if the coefficient before the treatment indicator is significant. Each subject will have a random intercept. The model is given by
$$\text{logit}(\text{outcome}) \sim 1 + \text{treatment} + (1|ID)$$
- **Continuous Outcomes**
 - We will perform repeated measure linear regression by regressing the continuous outcome (percentage outcome will be log-transformed) on the treatment indicator and test if the coefficient before the treatment indicator is significant. Each subject will have a random intercept. The model is given by
$$\text{outcome} \sim 1 + \text{treatment} + (1|ID)$$
- **Categorical Outcomes**
 - We will perform repeated measure multinomial regression by regressing the categorical outcome on the treatment indicator and test if the coefficient before the treatment indicator is significant. Each subject will have a random intercept. The model is given by
$$\text{multi-logit}(\text{outcome}) \sim 1 + \text{treatment} + (1|ID)$$

Quality Check

For patients who dropped out during the study, normalize endpoints to the same scale as the other patients, depending on the type of endpoints.

Sensitivity Analyses

1. Exclude participants who dropped out from all analyses.
2. Exclude participants who had endpoint data drawn "off-schedule" (troponin T, symptoms, etc.) from individual endpoint analyses.
3. Exclude participants who had an abnormality with their troponin T blood draw from troponin T-related analyses.
4. Test for difference by order of randomization (UF profiling --> conventional --> UF profiling --> conventional) vs. (conventional --> UF profiling --> conventional --> UF profiling)
5. Test for difference by clinic (site 1 vs. site 2)

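### If the five-level symptom items are the SAP's categorical outcome, its multinomial model has four treatment coefficients, ignores their order, and departs from the protocol's binary analysis

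*Combined protocol and SAP*

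**What the plan says.** The SAP (Primary Analysis, Categorical Outcomes) gives one rule: "We will perform repeated measure multinomial regression by regressing the categorical outcome on the treatment indicator". The analyst is then to "test if the coefficient before the treatment indicator is significant". The formula is a multi-logit link with an intercept, treatment and one random intercept per subject. No reference category, joint test or use of ordering is given, and no endpoint is assigned to the rule.

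The protocol makes symptoms the seventh secondary endpoint (4.2.2): "Patient-reported symptoms: measured after the 1st HD treatment each week; see Appendix B for data collection form". The Appendix B form instructs: "Please respond to each statement by marking one box per row". Each of its 12 named symptoms and the write-in item has five boxes, running none, mild, moderate, severe, very severe.

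Protocol 10.4.3 places symptoms among the binary secondary endpoints: "symptom occurrence between HD treatments will be performed using generalized estimating equations". Protocol 10.4.1 plans "generalized estimating equations for categorical outcomes" in general.

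**The concern.** The SAP uses the same test sentence for binary, continuous and categorical outcomes. It works for the first two, where treatment has one coefficient. It does not work for a five-level multinomial logit, where treatment has a separate coefficient for each non-reference level. An analyst could report one chosen contrast, any of the four, or a joint test, and each gives a different p-value.

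The model also discards information. Shuffling the severity labels would leave its fit unchanged, although the form was built to grade severity.

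The protocol describes a different analysis of the same form, with a yes/no outcome and a marginal model. Patient-reported outcomes are part of the study objective (section 3), so the symptom analysis should not be left to a choice made after the results are seen.

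**Working it through.** **Inputs from the documents.** Five ordered levels per item and 13 severity items (Appendix B). Three forms per phase (7.3.7) and two phases per arm, so 6 forms per patient per arm and 6 × 30 = 180 forms per arm. Two-sided 0.05 (10.4.1). Correction for multiple testing is described only for the three primary outcomes (10.4.9).

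**The plan's own power figure.** Section 10.5 gives no power, effect size or response distribution for symptoms. Its nearest figure, 80% power for a 5.9 mmHg difference in nadir systolic BP (SD 8), reproduces as 80.2% with a two-sample t-test at 30 per arm. I take 80% as the reference level; applying it to symptoms is my assumption.

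**Number of coefficients.** A baseline-category logit with K levels has K − 1 treatment coefficients: 5 − 1 = 4. Over 13 items that is 13 × 4 = 52 possible tests instead of 13.

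**False positives if each coefficient is tested.** With independent tests, 1 − 0.95^4 = 0.185 per symptom. The four share a reference category, so they are not independent. A no-effect simulation (180 independent forms per arm, assumed severity 60/22/11/5/2%, datasets with an empty cell dropped) gave about 13.6%.

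**Power if a joint test is used.** Find the noncentrality λ at which a 1-df chi-square test has the reference power, then compute P(χ²(k, λ) > χ²(k, 0.95)) for k df. The critical values are 3.841, 5.991, 7.815 and 9.488 for 1 to 4 df. This assumes a proportional-odds shift, so that the 1-df test captures all of the signal.

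| Power on 1 df | λ | Joint test | Power | Loss (points) |
|---|---|---|---|---|
| 80% | 7.849 | 4 df (5 levels in use) | 59.5% | 20.5 |
| 80% | 7.849 | 3 df (4 levels) | 64.5% | 15.5 |
| 80% | 7.849 | 2 df (3 levels) | 70.9% | 9.1 |
| 50% | 3.841 | 4 df | 30.8% | 19 |
| 60% | 4.899 | 4 df | 38.9% | 21 |
| 70% | 6.172 | 4 df | 48.3% | 22 |
| 90% | 10.507 | 4 df | 74.0% | 16 |

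**Check with repeated forms.** I simulated 30 patients with 6 forms per arm, a patient random intercept and a proportional-odds effect. Within-patient 1-df mean-score tests were compared with unordered association tests. With well-spread categories power was 78–82% against 58–61%, a loss of about 20 points. With sparse upper categories it was 79–84% against 63–70%, a loss of 11 to 19 points.

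**Where the protocol's binary analysis stands.** Illustrative scenario, all assumed: 180 independent forms per arm, control severity 60/22/11/5/2%, cumulative odds ratio 0.55.

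- Control, any symptom: 0.40, odds 0.40/0.60 = 0.667.
- UF profiling: odds 0.667 × 0.55 = 0.367, probability 0.367/1.367 = 0.268. Difference 0.132.
- Standard errors: 0.0497 under the null, 0.0492 under the alternative.
- Power: Φ((0.132 − 1.96 × 0.0497)/0.0492) = Φ(0.70) ≈ 76%.

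In 20,000 simulated datasets of this scenario the joint unordered test had about 56%, the ordinal score test 77% and any-versus-none 76%. At least one arm had an empty category in 16% of datasets; a category was missing from both arms in 0.3%.

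**The case against.** The strongest reply is that the SAP never says symptom severity is a categorical outcome. The only text that types the endpoint is protocol 10.4.3, which calls it binary. Read that way, symptoms fall under the SAP's random-intercept logistic rule and the categorical rule may apply to nothing. This stands as a caution: the link is a strong inference, not a stated fact. But if symptoms are not meant, the categorical rule has no evident endpoint, and that also needs saying.

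A second reply is that the binary analysis already in the protocol gives up almost nothing. In the scenario above that is correct (76% against 77%). The power loss therefore belongs to the joint multinomial test and not to the protocol's analysis.

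A reader might also infer four stronger things that the documents do not support:

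- **A fixed 20-point loss.** The figure needs an 80% reference, proportional odds, all five levels in use and a joint test that the SAP does not name. With sparse severe responses the loss is smaller. Without proportional odds the ordinal advantage can shrink or reverse.
- **An undefined patient intercept.** One intercept shared across the four logits is a definable model, though restrictive and dependent on the reference category.
- **Convergence failure.** The calculations do not show it. An empty category in one arm in 16% of assumed datasets is a sign of sparse data, not evidence that the mixed model cannot be fitted.
- **A threat to the primary results.** Symptoms are secondary, and 10.4.1 calls this a small pilot in which estimates and intervals will inform interpretation.

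**Conclusion.** The concern holds in conditional form. If the categorical rule is meant for the Appendix B items, the test it describes does not exist as a single quantity, and the model ignores the order of the scale. Those two statements rest on the documents alone.

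The sizes rest on assumptions. The 18.5% false-positive figure assumes independent coefficient tests. The loss of about 9 to 22 points assumes a joint test and a proportional-odds shift, and covers three to five levels in use at the 80% reference and a reference power of 50% to 90% with all five levels.

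The SAP and protocol 10.4.3 must be reconciled whichever reading is right. Even if symptoms are dichotomised, one text plans GEE and the other a subject-specific random intercept; that mismatch reaches the other binary endpoints too. This should be corrected before unblinding, but it is not a critical flaw.

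**What to change.** 1. In the SAP, name the symptom endpoint and replace the multinomial rule for severity with a cumulative-logit mixed model: each item's five ordered levels, a patient random intercept, and one treatment odds ratio with its 95% confidence interval.
2. Add a check of proportional odds and a rule, fixed before unblinding, for collapsing sparse upper levels.
3. Keep the protocol's any-versus-none occurrence analysis. State which of the two is the main symptom analysis and which is supportive.
4. Put the same text in protocol 10.4.3 and the SAP, including whether the binary model is GEE or random-intercept logistic.
5. If any other endpoint is meant to be categorical, name it; otherwise delete the multinomial rule.

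The cost is wording in the SAP and 10.4.3, with the IRB review that 13.2 requires for a protocol amendment. No data collection or trial conduct changes. The small statistical downside is reliance on proportional odds. The check in step 2 will have limited power if severe responses are few, which is a further reason to keep the binary analysis beside it.

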7.2 LABORATORY PROCEDURES/EVALUATIONS

7.2.1 CLINICAL LABORATORY EVALUATIONS

Troponin T (blood sample): Blood samples for Troponin T measurement will be collected via the vascular access by dialysis clinic staff. Troponin T will be collected before and after the 7th HD treatment of each phase for the calculation of troponin T change (2 troponin T changes during UF profiled HD and 2 during control HD). Troponin T is the only laboratory test to be performed as part of the study.

Standard-of-care laboratory measurements: Study start will be timed so that standard-of-care monthly lab testing (electrolytes, albumin, complete blood count, Kt/V, iron stores, bone-mineral tests) will be drawn within 6 weeks prior to study start (baseline). A 24-hour urine collection will be performed during baseline to measure residual kidney function (mL urine/day). These standard-of-care laboratory measurements will be performed as part of routine clinical care and are not study-specific.

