7.2.2 OTHER ASSAYS OR PROCEDURES

TTE: Patients will undergo intradialytic TTE at baseline (within 6 weeks prior to study start) and 30 minutes prior to HD end ("peak stress") during treatment 7 of the first phase of each treatment type (once during conventional and once during UF profiled treatment) (1 TTE during UF profiled HD and 1 during control HD). Study TTEs will be performed by a trained sonographer with a Philips CX50 ultrasound system (Philips North America).

Blood volume monitoring: Blood volume monitoring will be performed continuously throughout each study treatment via a Crit-line™ (standard-of-care non-invasive relative blood volume monitoring tool used as part of standard dialysis treatments).

Plasma refill test: Using the blood volume monitor, a plasma refill test will be performed 10 minutes before HD end during the 7th treatment of each phase. At the start of the treatment, UF time will be set 10 minutes less than treatment time. When the dialysis UF ends, study staff will document the hematocrit (%) from the blood volume monitor, and when the treatment ends, document the blood volume monitor hematocrit (%) again. Plasma refill tests are part of the blood volume monitoring protocols at the selected units and are familiar to staff.

Patient acceptance: At the end of the 9th study treatment of each phase, study staff will ask the participant the following question: "If recommended by your physician, would you be willing to adopt the HD prescription you have received during the last 9 treatments?"

Symptom assessment: At the conclusion of the 1st study treatment each week, study staff will ask patients to complete a symptom questionnaire (Appendix B).

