7.3.7 SCHEDULE OF EVENTS TABLE

Procedures	Baseline (6 week prior to study start)	Every study HD treatment	Before and after 7 th HD treatment of each phase	During 7 th HD treatment of each phase (twice per treatment type)	During 7 th HD treatment in the first phase of each treatment type (once per treatment type)	After 9 th HD treatment of each phase	After 1st HD treatment of each week (3x/phase)
Baseline laboratory testing	X						
Baseline history and physical	X						
Pregnancy status inquiry	X						
BP monitoring	X	X					
Weight monitoring	X	X					
Blood volume monitoring	X					X	
Troponin T laboratory testing			X				
TTE	X				X		
Plasma refill test	X			X			
Patient acceptance assessment						X	
Symptoms assessment						X	

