10.5 SAMPLE SIZE

This cross-over study is designed as a pilot study to test for efficacy signals. However, with its cross-over design in which each participant acts as his or her own control, we are powered to detect clinically and statistically significant differences across arms within patients. With a sample size of 30, we have 80% power to detect a 5.9 mmHg difference in nadir SBP (S.D. 8), a ≥ 0.07 ng/mL troponin T difference (S.D. 0.1), a 2.2% strain difference (S.D. 3), and 4% ejection fraction difference (S.D. 5); all clinically meaningful differences. We have 80% power to detect a 31% absolute difference in the binary endpoint of Troponin T change >0.1 ng/mL (event rate=20%).

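### Sensitivity analyses 2 and 3 drop the whole participant from an endpoint when one item is off-schedule or faulty, rather than only the affected value

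*Combined protocol and SAP*

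**What the plan says.** The SAP lists five sensitivity analyses. Item 2 begins "Exclude participants who had endpoint data drawn 'off-schedule" and gives troponin T and symptoms as examples. Item 3 is "Exclude participants who had an abnormality with their troponin T blood draw from troponin T-related analyses". Both name the participant as the unit to remove. Both also confine the removal: item 2 to the endpoint concerned, item 3 to the troponin analyses. Neither off-schedule nor abnormality is defined, and no expected frequency is given.

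The endpoints are measured repeatedly:

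- **Troponin T** (protocol 7.2.1): "Troponin T will be collected before and after the 7th HD treatment of each phase for the calculation of troponin T change", which gives "2 troponin T changes during UF profiled HD and 2 during control HD".
- **Symptoms** (protocol 7.3.7): the schedule column reads "After 1st HD treatment of each week (3x/phase".
- **Intradialytic echocardiography** (protocol 7.2.2): "1 TTE during UF profiled HD and 1 during control HD".

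The SAP's primary models have a treatment term and a random intercept per participant, with no exclusion for timing or draw quality. Protocol 5.3 says a missed treatment is not made up and simply leaves that treatment's data missing; the participant's other data stay.

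**The concern.** The purpose of items 2 and 3 is to show whether mistimed or faulty values drive the result. As written, each run changes two things at once: it removes the suspect values, and it removes all the sound values of the same people under both treatments. If the estimate moves, the cause cannot be identified. If an interval widens or significance is lost, that may reflect only the smaller sample.

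Nothing in the model requires this. A random-intercept model uses whatever observations a participant has. The rule also sits oddly beside protocol 5.3. A participant whose troponin pair in one phase was never drawn keeps the other three changes in analysis 2. One whose pair was drawn off-schedule loses all four. A late value costs more than a missing one.

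Troponin T change is one of the three primary endpoints (protocol 4.2.1), so it deserves a robustness check that can be interpreted.

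**Working it through.** **Inputs from the documents.** 30 completing participants (protocol 5.3, 10.5). Troponin: 2 changes per treatment × 2 treatments = 4 pre/post pairs each, from 8 draws; 120 pairs in all. Symptoms: 3 forms per phase × 4 phases = 12 each; 360 in all.

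**Inputs assumed.** Error rate *q* per item of 2%, 5% or 10%; errors independent within a participant, then clustered. The documents give neither.

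**The plan's own figure.** Protocol 10.5 states "With a sample size of 30, we have 80% power to detect a 5.9 mmHg difference in nadir SBP (S.D. 8"). A two-sample *t* calculation with 30 per arm and two-sided 5% gives power 0.802, so the figure reproduces on that basis. The same formula gives 0.76 for the stated 0.07 ng/mL troponin difference (SD 0.1). The plan gives no figure for the size of the sensitivity sets.

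**Participant-level rule, independent errors.** A participant stays only if all *k* items are sound, so the expected number kept is 30 × (1 − *q*)^*k*.

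| *q* | Troponin, *k* = 4 | Symptoms, *k* = 12 |
|---|---|---|
| 2% | 30 × 0.98^4 = 27.7 | 30 × 0.98^12 = 23.5 |
| 5% | 30 × 0.95^4 = 24.4 | 30 × 0.95^12 = 16.2 |
| 10% | 30 × 0.90^4 = 19.7 | 30 × 0.90^12 = 8.5 |

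Item 3 speaks of the blood draw. If the error rate applies to each of the 8 draws, the troponin column becomes 25.5, 19.9 and 12.9.

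**Participant-level rule, clustered errors.** With a beta-binomial and within-participant correlation ρ = 0.3, set a = *q*(1 − ρ)/ρ and b = (1 − *q*)(1 − ρ)/ρ. The chance of no error in *k* items is the product over j = 0 to *k* − 1 of (b + j)/(a + b + j). At 10%, a = 0.233 and b = 2.1. For *k* = 4 the product is 0.900 × 0.930 × 0.946 × 0.956 = 0.757, so 22.7 participants remain. For *k* = 12, 18.5 remain. At 5% the counts are 26.2 and 23.7.

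**Value-level rule, independent errors.** Only the affected pair or form goes, so a share 1 − *q* of the values is kept. The chance of at least one sound troponin pair under each treatment is (1 − *q*²)².

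| *q* | Pairs kept of 120: value rule / participant rule | Participants with pairs under both treatments, value rule | Forms kept of 360: value rule / participant rule |
|---|---|---|---|
| 2% | 118 / 111 | 30.0 | 353 / 282 |
| 5% | 114 / 98 | 29.9 | 342 / 195 |
| 10% | 108 / 79 | 29.4 | 324 / 102 |

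The participant-rule entries are 4 (or 12) times the expected number of participants kept.

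**Effect on precision, for scale only.** On the two-sample basis that reproduces protocol 10.5, power for 0.07 ng/mL falls from 0.76 with 30 to 0.66 with 24 (*q* = 5%) and 0.58 with 20 (*q* = 10%). With 29 it is 0.745, which is about where the value-level rule leaves it at 10%. This formula is not the planned mixed model, and it treats a partly observed participant as complete, so only the contrast matters.

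**Echocardiography.** With one scan per treatment, losing either scan leaves data under one treatment only. The number with both scans is 30 × 0.90² = 24.3 at 10% under either rule, so the choice of unit matters little there.

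**The case against.** The strongest case for the text as it stands is that these are sensitivity analyses and the rule is a conservative choice. The exclusion is limited to the endpoint concerned, the primary analysis keeps everyone, and no decision depends on these runs. Protocol 10.4.1 calls the study a small pilot to be read through estimates and intervals. Removing whole participants preserves the existing within-person comparison in those who remain, and it also removes other values from someone whose draw problem may recur, for instance because of the vascular access. An unchanged estimate would still be informative. All of this stands. It limits the importance of the point and is a reason to keep the participant-level run as a supplement, but it does not make that run able to isolate the suspect values.

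The size is also open to challenge. The error rates and independence are assumptions, and problems with clinic, staff or access could well cluster, which softens the loss considerably. With the two terms undefined, the true rate may be very low. That stands too, and is why a range is shown.

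A reader might infer three stronger things that the documents do not support:

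- **That a modest error rate would empty the analysis.** Under independence, the expected number left falls below one only above about 25% per form for symptoms, 35% per draw for troponin, or 57% per troponin pair.
- **That those who remain are simply the most punctual patients.** Clinic staff draw the troponin samples (protocol 7.2.1) and study staff administer the forms (7.2.2), so errors may have little to do with the patient.
- **That the primary result is at risk.** The primary models apply neither exclusion.

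**Conclusion.** The point holds as a minor one. Items 2 and 3 use the participant as the exclusion unit where the model, and the protocol's own handling of missed treatments, would let the single observation be the unit. Sound data from both arms are lost, and a changed result cannot be attributed to the suspect values.

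At independent error rates between 2% and 10%, the expected loss is about 2 to 10 of 30 participants for troponin pairs and about 6 to 22 for symptoms. At 10% with clustering (correlation 0.3) it is about 7 and 11 to 12. Those losses rest entirely on assumed rates and correlation; the choice of unit itself is plain from the SAP. Only the two sensitivity analyses are affected.

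**What to change.** In sensitivity analyses 2 and 3, exclude only the affected pre/post troponin pair or symptom form, keep the participant's remaining observations in the same random-intercept model, and report the number of observations excluded by treatment. State what counts as off-schedule and as an abnormal draw, so that the exclusions can be applied the same way by anyone. The participant-level exclusion may stay as a labelled supplement.

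The cost is two reworded SAP lines, short definitions and one small table; no new data are needed. The downside is some imbalance between treatments in the values kept and, occasionally, a participant with data under one treatment only, who adds little to the within-person comparison.
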